### **6.3 Medical history and concomitant diseases**

Medical history (with the exception of that related to epilepsy) and concomitant diseases are not collected in this study.

Concomitant medical procedures will be listed on the All Subjects Documented set including the procedure, detail of what the procedure is primarily related to, and the date of the procedure.

### **6.4 Prior and concomitant medications**

Medications will be reviewed during the DEM to ensure correct classification. In addition, historical and concomitant medications will be reviewed to ensure documentation in the correct CRF pages. Historical medications are defined as medications discontinued prior to the date of first BRV administration. Medications at study entry are defined as those being taken on the same day as first BRV administration. Concomitant medications are medications taken at least 1 day in common with the study medication dosing period. In other words, those that started on or prior to the date of first BRV administration, and have an end date on or after the date of first BRV administration or are ongoing; or those starting after the first BRV administration and on or before last BRV administration.

Non-AED historical medications, those stopped before the date of first BRV administration, should not be collected in the CRF.

As there are snapshot analyses throughout the study and data entry is ongoing, any non-coded terms at the time of reporting will report the WHODD Anatomical Main Group [Level 1], Pharmacological Subgroup [Level 3] and PT as UNCODED in the tables and listings.

The number and percentage of patients with each of the following medication types will be summarized overall and by WHODD Anatomical Main Group [Level 1], Pharmacological Subgroup [Level 3] and PT.

- Number and percentage of patients with AED concomitant medications (including LEV)
- Number and percentage of patients with non-AED concomitant medications

Where necessary, PTs may be collapsed into AED PT categories for study reporting and where applied this will be added as a footnote on the output. In addition, LEV use will be combined with other AED medications and reported in the table of AED concomitant medications.

Patients documented as having used a vagus nerve stimulation (VNS) magnet will be considered as having active use on the date of first BRV administration and during the study. Hence, VNS use is counted as an AED for AEDs taken at study entry. As historical AEDs are defined as medications discontinued prior to the date of first BRV administration, VNS use at study entry will not be counted as a historical AED. Lifetime AEDs are defined as a sum of the historical AEDs and AEDs taken at study entry. As LEV can be included in both historical AEDs and AEDs at study entry, it will only be counted once in the calculation of Lifetime AEDs.

VNS use, number of historical AEDs, number of AEDs at study entry, Lifetime AEDs and LEV use will be summarized as follows:

- Number of patients with/without a VNS magnet
- Number of patients with historical and LEV use at study entry
- Number of historical AEDs, presented using summary statistics and the following categories (0, 1, 2, 3, 4, 5, 6, >6 and the subgroup categories 0-3, 4-6 and >6)
- Number of AEDs at study entry, presented using summary statistics and the following categories (0, 1, 2, 3 and >3)
- Number of Lifetime AEDs, presented using summary statistics and the following categories (0, 1, 2, 3, 4, 5, 6, >6 and the subgroup categories 0-3, 4-6 and >6)

The summaries above will be repeated for the subgroups of patients with and without VNS use, and with and without historical LEV.

The following listings will be provided:

- Concomitant medications glossary. To include the WHODD Anatomical Main Group [Level 1], Pharmacological Subgroup [Level 3], PT, and Reported Term (Medication)
- By-patient listings of the WHODD Anatomical Main Group [Level 1], Pharmacological Subgroup [Level 3], PT, reported term (medication), dose, unit, frequency, formulation, indication, start and end dates/ongoing (and including the reason for discontinuation for LEV if applicable) will be presented for the following medications for the All Subjects

Documented set

- Concomitant AED medications (including LEV use)
- Concomitant non-AED medications
- Historical LEV use (including the reason for discontinuation)

- By-patient listing of VNS use, historical AEDs, historical LEV use, LEV use at Study Entry, and the number of historical and AEDs at Study Entry.

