The efficacy of BRV for the adjunctive therapy of POS was established in 3 Phase 3 randomized, double-blind, placebo-controlled, fixed-dose, multicenter studies in subjects 16 years of age and older. The daily dose of BRV ranged from 5 to 200mg/day across these studies. All studies had an 8-week Baseline period followed by a 12-week treatment period with no up-titration. A total of 1558 patients received study drug, of which 1099 received BRV. Study enrollment criteria required that patients had uncontrolled POS despite treatment with either 1 or 2 concomitant antiepileptic drugs (AEDs). Patients were required to have at least 8 POS events during the Baseline period. Adjunctive BRV administration at doses of 50mg/day to 200mg/day without titration resulted in statistically significant and clinically relevant reductions in seizure frequency, including seizure freedom. Brivaracetam was effective and well tolerated when started at these therapeutic doses. Low incidences of adverse events (AEs) and low study discontinuation rates due to AEs were also observed with BRV. A recent small, open-label, Phase 3 study evaluating nonpsychotic behavioral AEs in patients receiving levetiracetam (LEV) who switched to BRV showed that, at the end of the 12-week treatment period, 93.1% patients (27/29) who switched to BRV had clinically meaningful reductions in behavioral AEs, which suggest that patients experiencing behavioral AEs associated with LEV may benefit from switching to BRV (Yates et al, 2015).

EP0077 is the first postauthorization observational study of BRV in the real world, and is designed to collect information on the effectiveness in patients with POS who are treated with BRV in clinical practice after the product is marketed in the European Union.

EP0077 is a postmarketing, multinational, multicenter, noninterventional study (NIS) conducted at specialized sites in approximately 10 European countries, with a 12-month Observation Period. Patients will be treated according to usual medical diagnostic procedures and therapy; commercially available BRV will be prescribed according to normal clinical practice and the current Summary of Product Characteristics (SmPC) in Europe for BRV. The prescription of BRV is clearly separated from the decision to include the patient in the study. No additional diagnostic or monitoring procedures are applied to the patients.

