**Table 17–1: Recommended schedule of study assessments**

Assessments	Visit 1 a Baseline/Day 1 First Day of BRV Treatment	Visit 2 3 Months (Approximately 3 months after Baseline according to routine practice b )	Visit 3 6 Months (Approximately 6 months after Baseline according to routine practice b )	Visit 4 c 12 Months (Approximately 12 months after Baseline according to routine practice b ) End of Observation/ Withdrawal Visit
Recording of AEs	X h	X	X	X
QOLIE-31-P	X	X	X	X
EpiTrack cognition assessment	X		X	X
CGIC		X	X	X
PGIC		X	X	X
Withdrawal criteria		X	X	
Study termination				X

AE=adverse event; AED=antiepileptic drug; BRV=brivaracetam; CGIC=Clinical Global Impression of Change; PGIC= Patient’s Global Impression of Change; QOLIE-31-P=Patient Weighted Quality of Life in Epilepsy Inventory-Form 31

a Visit 1 will be performed after the decision is taken to start adjunctive BRV therapy. Treatment with BRV should be initiated according to routine clinical practice. If the first dose of BRV is given on the same day as Visit 1, it should be administered after Baseline assessments are complete.

b The frequency of visits after Visit 1 will be based on local clinical practice and the patients’ requirements. The clinical procedures performed at each visit will also follow local clinical practice.

c For patients who discontinue early, the treating physician should collect data as specified for Visit 4 as a Withdrawal Visit.

d To include year of first epilepsy diagnosis, lifetime AEDs, etiology. Dates of use of levetiracetam with dosages and reason for discontinuation will be recorded when applicable.

e The treating physician will explain the importance of diary completion to the patient and will review his/her diary at each visit.

f The treating physician will evaluate at each visit the frequency and type of seizures experienced by the patient since the previous study visit. At Baseline, seizure frequency will be based on the previous 3 months to estimate the frequency per 28 days.

g Record name of AED and dose, and any changes after Visit 1.

h Adverse events will be recorded from the moment data consent is obtained.

---

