#### **4.2.2 Times and Dates**

Partial dates may be imputed for statistical analyses for specific outcomes according to the following rules. There will be no imputation of missing times. In general, imputed dates will not be shown in listings with the exception of showing imputed dates alongside partial dates for key derivations.

Imputation of partial first BRV administration date:

- If the day of first BRV administration is missing and the month and year are the same as the month and year of Visit 1 then the date of Visit 1 will be imputed as the date of first BRV administration. Otherwise impute 1st of the month.
- If the day and the month of first BRV administration are missing then no imputation of the partial date will be done.

Imputation of partial start dates:

- If only the month and year are specified and the month and year of first dose is not the same as the month and year of the start date, then use the 1st of the month.
- If only the month and year are specified and the month and year of first dose is the same as the month and year of the start date, then use the date of first BRV administration.
- If only the year is specified, and the year of first dose is not the same as the year of the start date, then use January 1st of the year of the start date.
- If only the year is specified, and the year of first dose is the same as the year of the start date, then use the date of first BRV administration.
- If the start date is completely unknown, then use the date and time of first BRV administration.

Imputation of partial end dates:

- If only the month and year are specified, then use the last day of the month.
- If only the year is specified, then use December 31st of that year.
- If the stop date is completely unknown, do not impute the stop date.

The imputation rules should not create an inconsistency in the data.

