#### **4.8 Examination of subgroups**

- Age at Visit 1 (<65 and ≥65 years).
- Time since first diagnosis of epilepsy (0-<1 years, 1-<5 years, 5-10 years, >10 years): Defined in [Section 6.2](#)
- Number of AEDs at study entry (0, 1, 2, 3 and >3 AEDs) : Defined in [Section 6.4](#)
- Number of Historical AEDs (0 or 1 or 2 or 3, 4 or 5 or 6, >6): Defined in [Section 6.4](#)
- Historical Levetiracetam (LEV) use (Yes, No): Defined in [Section 6.4](#)
- Number of Lifetime AEDs (0 or 1 or 2 or 3, 4 or 5 or 6, >6): Defined in [Section 6.4](#)
- 28-day Baseline all seizures frequency (≤5, >5-10, >10): Defined in [Section 8.2.2.1](#)

The number of patients in the subgroup categories listed above will be examined at the DEM meeting to ensure sufficient patients exist in each category for statistical analysis of the primary and secondary variables by subgroup to offer meaningful analyses. For example, if it is deemed that there are an insufficient number of patients in the ≥65 years age at Visit 1 category, then the age at Visit 1 categories may be amended to use <60 and ≥60 years instead.

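### The *No* row of the historical LEV subgroup mixes LEV-naive patients with patients still taking LEV on the day BRV starts, so the contrast by LEV exposure is diluted

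*SAP*

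**What the plan says.** SAP 4.8 lists one LEV subgroup, "Historical Levetiracetam (LEV) use (Yes, No"), and refers to SAP 6.4 for its meaning. Section 6.4 separates two classes by calendar day:

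- Historical: "Historical medications are defined as medications discontinued prior to the date of first BRV administration".
- At study entry: "Medications at study entry are defined as those being taken on the same day as first BRV administration".

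The two classes can overlap for one patient: "As LEV can be included in both historical AEDs and AEDs at study entry", LEV is counted once among lifetime AEDs.

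The Section 4.8 subgroups feed three sets of effectiveness tables: 12-month retention (SAP 8.1.3), and absolute POS reduction and seizure freedom (SAP 8.2.2.3). LEV at study entry is counted and listed by patient in Section 6.4, but it defines no effectiveness subgroup. The lifetime AED subgroup is a number of drugs and does not identify LEV.

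For incomplete stop dates, SAP 4.2.2 says: "If only the month and year are specified, then use the last day of the month". The same section adds that imputation should not make the data inconsistent.

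The protocol gives LEV some prominence. Its background section reports an earlier switch study and suggests that "patients experiencing behavioral AEs associated with LEV may benefit from switching to BRV". Footnote d of Table 17–1 adds: "Dates of use of levetiracetam with dosages and reason for discontinuation will be recorded when applicable".

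**The concern.** A reader of a table split by historical LEV use will be interested in patients with LEV exposure against patients without it. The definition does not produce that split. It asks only whether a LEV episode had ended before the first BRV date. Patients who come to BRV straight from LEV with any overlap, even of one day, sit in *No* beside patients who never had the drug. A patient otherwise identical, whose LEV stop date is one day earlier, sits in *Yes*.

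At stake is the reading of the *No* row. If LEV-exposed and LEV-naive patients differ in retention or seizure control, the row averages the two and the difference between rows shrinks by an amount that the effectiveness tables do not show. The patients placed there include some of the switchers whom the protocol's background describes.

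**Working it through.** **1. The coding rule.** Take first BRV as Day 1 and a patient with a single LEV episode.

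| LEV stop | Before first BRV date? | Coded |
|---|---|---|
| Day −1, complete date | yes | *Yes* |
| Day 1 (same-day switch) | no | *No* |
| Day 15 (cross-taper) | no | *No* |
| Ongoing | no | *No* |
| Never took LEV | – | *No* |

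A patient on LEV at Day 1 who also has an earlier ended episode is *Yes*. So *No* collects single-episode patients with LEV on Day 1, plus the LEV-naive.

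**2. Month-only stop dates.** Suppose BRV starts on 15 March 2018 and the LEV stop is known only as March 2018. The end-date rule gives 31 March, which is not before 15 March, so the patient is *No*. The result is the same for any BRV start day in that month, because the imputed stop is never earlier than the start. This holds only if the rule is applied to this classification.

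**3. Dilution.** Let p_E be the outcome rate in every LEV-exposed patient, p_N the rate in LEV-naive patients, and c the share of *No* patients on LEV at entry. Then

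- *No* row = c·p_E + (1 − c)·p_N
- contrast shown = *No* row − p_E = (1 − c)·(p_N − p_E)

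The documents give neither c nor the rates, so the shares below are assumptions. Historical LEV is set at 60% of the FAS in the first three lines and 50% in the last.

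| LEV at entry only / never (share of FAS) | c | 1 − c | True 10 points shown as | True 20 points shown as |
|---|---|---|---|---|
| 5% / 35% | 5/40 = 12.5% | 0.875 | 8.8 | 17.5 |
| 10% / 30% | 10/40 = 25% | 0.75 | 7.5 | 15.0 |
| 20% / 20% | 20/40 = 50% | 0.50 | 5.0 | 10.0 |
| 40% / 10% | 40/50 = 80% | 0.20 | 2.0 | 4.0 |

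Example, third line: with retention of 50% if exposed and 70% if naive, the *No* row is 0.5 × 50 + 0.5 × 70 = 60%. The contrast is 60 − 50 = 10 points instead of 20.

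**4. Precision after a split.** The plan's only sample-size figure reproduces: 1.96² × 0.25 / 0.05² = 384.2, so 385. It does not depend on this point and serves here only as a base. With the 20% / 20% split of 385:

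- *No* row: 0.40 × 385 = 154 patients. At 55% retention the 95% half-width is 1.96 × √(0.55 × 0.45 / 154) = 7.9 points.
- LEV-naive row: 0.20 × 385 = 77 patients. At 60% it is 1.96 × √(0.6 × 0.4 / 77) = 10.9 points; at 70%, 10.2 points.

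These use the normal approximation. If all 100 German patients also enter the FAS (385 + 100 = 485), the naive row has 97 patients and a half-width of 9.7 or 9.1 points.

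**The case against.** The other side has several sound arguments.

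- **The label is accurate.** The variable is called historical, it is defined, and nothing in the documents calls *No* LEV-naive. This stands, but it does not unmix the row.
- **The mixing will be visible in part.** Section 6.4 counts LEV at study entry and repeats its summaries with and without historical LEV, so the number behind c will be reported. This stands. However, the count is on the SS while the effectiveness tables are on the FAS, and no outcome is shown separately for these patients.
- **The month-only rule may not apply.** SAP 4.2.2 says that dates may be imputed for specific outcomes and warns against inconsistency. Sections 6.2 and 8.3.4 call on it explicitly, but 6.4 does not for the historical class. The data evaluation meeting (DEM) also reviews medication classification and CRF pages. This largely stands: the risk is that the case is left unstated, not that misclassification is certain.
- **Importance is limited.** No objective concerns LEV switching, the analyses are descriptive and exploratory, and the current protocol names no prior-LEV subgroup; that wording survives only as superseded text in the amendment log. This stands and sets the severity.

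A reader might also infer that every direct switch from LEV is coded *No*, or that the subgroup can show nothing about LEV. Neither follows. An overnight switch with a complete stop date is *Yes*, and the *Yes* row remains a valid group of patients with a LEV episode that ended before BRV.

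**Conclusion.** The *No* row pools two kinds of patient, and no other planned effectiveness subgroup separates them. That follows from the SAP text alone. The size rests on assumptions: under equal outcomes in all LEV-exposed patients, the contrast shown is (1 − c) of the true one, from 88% at c = 12.5% to 20% at c = 80%, with c unknown from the documents.

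A reader might infer that the contrast could change sign. The model above does not give that: for any c below 1 the sign is kept. A reversal would need the further assumption that patients on LEV at BRV start do worse than earlier LEV users by a sufficient margin, and the documents contain nothing on this.

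The point is minor. It affects how one exploratory subgroup is read and leaves the overall primary result untouched.

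**What to change.** In SAP 4.8, replace the two-level variable by three mutually exclusive levels, assigned in this order:

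1. LEV taken on the date of first BRV, regardless of any earlier ended episode.
2. LEV stopped before first BRV and not taken on that date.
3. Never LEV.

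The order is needed because Section 6.4 allows LEV to be in both classes.

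For a LEV stop known only as the month in which BRV starts, state that a record on the historical LEV page counts as stopped before first BRV unless the DEM review shows overlap, and that last-day-of-month imputation is not used for this variable. Use the same three levels in the Section 6.4 summaries.

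The cost is SAP wording and one derived variable, set before database lock. Both flags it needs are already in the by-patient listing of Section 6.4. The downside is three smaller rows with wider intervals: in the assumed 20% / 20% case, a half-width of about 10 to 11 points for 77 LEV-naive patients, against about 8 for the mixed row of 154.

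### Lifetime AEDs is a sum with a count-once rule for LEV only, so any other AED stopped and then restarted by study entry is counted twice and some patients move up a subgroup

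*SAP*

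**What the plan says.** SAP section 6.4 builds the variable from two lists.

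- Historical: "Historical medications are defined as medications discontinued prior to the date of first BRV administration".
- Study entry: "Medications at study entry are defined as those being taken on the same day as first BRV administration".
- Lifetime: "Lifetime AEDs are defined as a sum of the historical AEDs and AEDs taken at study entry".

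The sentence after the lifetime definition gives the only count-once rule for a drug: "As LEV can be included in both historical AEDs and AEDs at study entry, it will only be counted once". VNS, which the SAP counts as an AED, is handled separately in the same paragraph: "VNS use at study entry will not be counted as a historical AED". No rule covers any other AED.

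The variable is used in two places. Section 6.4 summarises it as a Baseline characteristic, with summary statistics, single categories from 0 to 6 and >6, and the grouped categories. Section 4.8 lists it as a subgroup: "Number of Lifetime AEDs (0 or 1 or 2 or 3, 4 or 5 or 6, >6". Section 8.1.3 repeats the 12-month retention analysis in each subgroup. Section 8.2.2.3 does the same for absolute reduction in partial-onset seizure frequency and for seizure freedom.

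**The concern.** The two lists are not mutually exclusive. One is defined by an episode that ended before first BRV, the other by use on the day of first BRV. A drug that was stopped and later restarted satisfies both, whichever drug it is. The LEV sentence shows that the authors saw the overlap, but the correction stops at LEV.

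The lifetime count is one of a few treatment-history markers in the plan. A one-sided error in it makes the described population look more heavily pretreated than it is. It also places some patients with fewer previous drugs in the rows for more drugs, which blurs any gradient across those rows. In addition, two programmers working from this text could derive different counts.

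**Working it through.** No figure in the plan depends on this count, so there is none to reproduce for the point itself. The sample-size figures supply the patient numbers used below, and they do reproduce:

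- n = 1.96² × 0.25 / 0.05² = 384.15, so 385 (stated 385).
- 385 / 0.9 gives 428 (stated 430, rounded up).
- 430 + 100 = 530, and 530 × 0.9 = 477 as a working size for the FAS.

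**Step 1: the rule applied to two patients.** Both have carbamazepine, valproate and LEV in the historical list, so three distinct AEDs.

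- Carbamazepine taken again at entry: sum = 3 + 1 = 4, category 4–6. Distinct count = 3, category 0–3.
- LEV taken again at entry: sum = 3 + 1 − 1 = 3, category 0–3.

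The same history gives a different subgroup depending only on which drug was restarted.

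**Step 2: who changes subgroup.** The cut-points lie between 3 and 4 and between 6 and 7.

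- One duplicate changes the category only at a distinct count of 3 (to 4) or 6 (to 7).
- Two duplicates change it only at 2, 3, 5 and 6.
- In the single-category summary, each duplicate moves the patient up one category unless already at >6. The mean rises by the average number of duplicates per patient.

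**Step 3: how many patients.** Share reclassified = (share with one re-used AED other than LEV) × (share with a distinct count of 3 or 6). Neither input is in the documents. Two sets of assumptions give a range.

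- Set A: re-use in 5% to 20%, and 15% to 35% at a cut-point. This gives 0.05 × 0.15 = 0.75% to 0.20 × 0.35 = 7.0%, or about 4 to 33 of 477 (3 to 27 of 385).
- Set B: re-use in 10% to 30%, and true counts roughly Poisson with mean 4, 5, 6 or 7, for which P(3) + P(6) = 0.300, 0.287, 0.250 or 0.201. This gives 0.10 × 0.201 = 2.0% to 0.30 × 0.300 = 9.0%, or about 10 to 43 of 477.

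Together, roughly 1% to 9%.

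**Step 4: effect on subgroup retention.** Assume 385 patients in equal thirds (128.3 each), true retention of 80%, 70% and 60%, 25% to 40% of each of the two lower categories at its cut-point, re-use in 5% to 20%, and movers with the retention of the category they leave.

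- Largest case: 128.3 × 0.40 × 0.20 = 10.3 patients cross each cut-point.
- Row 4–6: (118.1 × 0.70 + 10.3 × 0.80) / 128.3 = 70.8%, against 70.0%.
- Row >6: (128.3 × 0.60 + 10.3 × 0.70) / 138.6 = 60.7%, against 60.0%.
- Smallest case (25%, 5%): 70.1% and 60.1%.
- Row 0–3 is unchanged at 80.0%.

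In this set-up the shift in the 4–6 row is (share at cut-point) × (re-use) × 10 points. At the 30% re-use of Set B it would therefore reach at most 0.40 × 0.30 × 10 = 1.2 points. For scale, the 95% CI half-width for a row of 128 at 70% is 1.96 × √(0.70 × 0.30 / 128) = 7.9 points.

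**Step 5: the overall estimate.** Overall 12-month retention and its CI do not use the lifetime count, so they do not change.

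**The case against.** The strongest objection is that the overlap may be peculiar to LEV. SAP section 8.3.4 says LEV is recorded separately in the CRF. The footnote on epilepsy history in Protocol Table 17–1 asks for dates, doses and reason for stopping for LEV alone. If the CRF prevents any other AED from appearing in both lists, nothing is counted twice. The CRF layout is not in the documents, so this remains possible. It does not alter what the text tells a programmer to do with a drug that is in both lists.

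The VNS rule also reasons that something in current use is not historical. Extended to drugs, that would remove the overlap. But the SAP does not extend it, and the LEV sentence says that a drug can be in both lists.

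A reader might infer a second route. The same protocol footnote describes the history to be collected: "To include year of first epilepsy diagnosis, lifetime AEDs, etiology". A site could list a drug still being taken, which would then be added twice. The documents largely close this route. A drug not yet discontinued does not meet the definition of historical, and the data evaluation meeting checks that entries are on the correct CRF pages. That check does not help with a restarted drug, because such a drug belongs on both pages.

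The analyses are descriptive and exploratory, and the expected shift is small beside the sampling error of a subgroup row. Both statements stand, and they limit the weight of the point.

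**Conclusion.** The point holds as a defect in a stated derivation rule. Section 6.4 read literally counts twice any AED other than LEV that was stopped before first BRV and is in use at entry, and the error is always upward. The clearer effect is on the Baseline description of Lifetime AEDs; the subgroup rows are affected less.

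The size is not known from the documents. Roughly 1% to 9% of the FAS would be in the wrong subgroup under the assumed rates of re-use and of counts at a cut-point. The likely effect on subgroup retention is under 1 percentage point if re-use is no more than 20% and retention differs by 10 points between rows.

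A reader might infer that patients in general are pushed into more refractory groups, or that the primary result is biased. The documents support neither reading. Only patients at a cut-point change row, the SAP does not label the rows by refractoriness, and overall 12-month retention and its CI are untouched. The subgroups based on historical AEDs and on AEDs at study entry are not affected either. Among the seizure-frequency tables, only absolute reduction and seizure freedom are broken down by this subgroup; percent reduction and response are not.

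**What to change.** In SAP section 6.4, replace the sum and the LEV sentence with one rule. Lifetime AEDs is the number of distinct AEDs, identified by WHODD preferred term after any collapsing of preferred terms, that appear in the historical or the study-entry records. Each is counted once, for every AED and not only LEV, and VNS is counted once as now. VNS has to be named, because a count of drug terms alone would drop it and move VNS users down by one. Leave the separate historical and study-entry counts otherwise unchanged.

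The cost is one sentence and a distinct count in programming. No new data are needed if historical AEDs are held by name, as the by-patient listing in section 6.4 suggests. If the CRF already prevents overlap, the results do not change.
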